Patients will be randomized by block randomization. On the first week of enrollment, the clinician will only enroll patients into the control arm. On the subsequent week, the clinician will only enroll patients into the intervention arm.

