4.3. Study outcome measures

Primary Endpoint

Rate of statin compliance, based on pharmacy refill records. Values per patient can range from 0-6 according to the number of refills.

Secondary Endpoints:

Rate of perceived side-effects from statin use, including muscle aches, fatigue, mental fog, and gastrointestinal upset.

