4.5. Sample size/Power calculation

This study is designed as a superiority trial. Based on prior literature, we estimate a 50% statin compliance rate with a standard deviation of 10% (2). We will set the minimal detectable effect at a 5% increase in statin compliance, with an $\alpha < 0.05$ and power of 0.9. Based on case-to-control ratio of 1:1, our total minimum sample size for the primary endpoint is 138. However, we will plan on a total sample size of 300 patients, to account for patients who drop out of the study as well as patients who will be excluded due to attaining an LDL-cholesterol of <2.6 mmol/L (100 mg/dL) on red yeast rice extract.

5. Participant entry

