6.2 Reporting procedures

Clinical Events Committee

The CEC is made up of cardiologists who are not participants in the trial. The CEC is charged with the development of specific criteria used for the adjudication of clinical events and clinical endpoints in the trial which are based on protocol.

The Clinical Events Committee will establish explicit rules outlining the minimum amount of data required, and the algorithm followed in order to classify a clinical event. All members of the Clinical Events Committee will be blinded to the treatment arm and the primary results of the trial.

The Clinical Events Committee will meet regularly to review and adjudicate all clinical events in which the required minimum data is available. The Committee will also review and rule on all deaths that occur throughout the trial.

Reports of clinical events should be submitted within 15 days of the Chief Investigator becoming aware of the event.

Local investigators should report any clinical events as required by their Local Research Ethics Committee, Sponsor and/or Research & Development Office.

Contact for reporting clinical events: [name]
Email: [contact]

Case report form

An online CRF form will be used throughout the study. This will be secure, and compatible with currently guidelines to ensure security of patient data. It will be managed via the Lithuanian University of Health Sciences Clinical Trials Unit , and data achieved securely.

7. Assessment and follow-up

Routine follow-up will be performed with a clinic visit at 6 months in the control group and at 2 months and 8 months in the intervention group. The CRF should be completed.

8. Statistics and data analysis

Data will be summarised as mean (SD) or median (interquartile range) for skewed data. Statistical comparisons will be undertaken using a paired Student's t-test (after log transformation if necessary) or nonparametric alternative if data are not normalised by log transformation. Kaplan-Meier survival analysis curves will be used to assess clinical event timelines.

9. Regulatory issues

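### Arms are allocated by clinician-week, but the planned comparison is a paired t-test with no term for week, clinician or centre, and the sample size assumes independent patients

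*Protocol*

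**What the plan says.** Protocol 4.2, under Randomisation, gives the method a name, "Patients will be randomized by block randomization", and then describes it: "On the first week of enrollment, the clinician will only enroll patients into the control arm". It continues: "On the subsequent week, the clinician will only enroll patients into the intervention arm". Only these two weeks are described. That the alternation continues through the six-month enrolment is an inference, but the protocol offers no other scheme.

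The primary endpoint in 4.3 is a refill count: "Values per patient can range from 0-6 according to the number of refills". For the analysis, section 8 states: "Statistical comparisons will be undertaken using a paired Student's t-test (after log transformation if necessary) or nonparametric alternative". It names no week, clinician, centre or cluster term.

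Section 4.5 sets out its assumptions as "we estimate a 50% statin compliance rate with a standard deviation of 10" per cent, a minimal detectable effect of 5 percentage points, alpha 0.05 and power 0.9. It concludes: "Based on case-to-control ratio of 1:1, our total minimum sample size for the primary endpoint is 138". The rise to 300 is justified only by dropout and by patients excluded for reaching the LDL goal on red yeast rice extract.

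**The concern.** Everyone a clinician enrols in a given week receives the same arm. Patients within a clinician-week are therefore not allocated independently of one another, and a test that treats them as independent has the right standard error only if outcomes do not vary between weeks beyond chance. Some week-to-week variation is plausible, because the intervention is a conversation led by the clinician (Appendix B) and its delivery may drift. If such variation exists, the interval for the arm difference is too narrow and the p-value too small.

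There is a second mismatch in the same sentence of section 8. A paired test needs a defined pairing, and the two arms contain different patients with no matching. A paired comparison of adjacent control and intervention weeks could respect the allocation, but the protocol defines nothing of the kind.

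**Working it through.** **1. Which formula gives 138.** Inputs from 4.5: difference 5, SD 10, alpha 0.05 (sidedness not stated), power 0.90, ratio 1:1. For two independent means, n per arm = 2(z_alpha + z_power)² × (SD/difference)².

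- One-sided: 2 × (1.645 + 1.282)² × 4 = 68.5, so 69 per arm and 138 in total. This matches exactly.
- Two-sided: 85 per arm, 170 in total. No match.
- Paired test, taking 10 as the SD of differences: 35 pairs one-sided or 43 two-sided. No match.

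So 138 treats patients as two independent groups. It contains neither a design effect nor the pairing that section 8 names.

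**2. How large the effect of week clustering could be.** From 4.2: 300 patients, four centres, six months (about 26 weeks). Assumed, because the protocol does not give them: ICC 0.01 to 0.05, and the number of clinicians. Formulas: m = 300 / number of clusters; design effect DE = 1 + (m − 1) × ICC; effective N = 300 / DE; true level of a nominal two-sided 5% test = 2[1 − Φ(1.96/√DE)].

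| Assumed pattern | Clusters | m | DE | Effective N | True level |
|---|---|---|---|---|---|
| Two clinicians per centre | 8 × 26 = 208 | 1.44 | 1.00–1.02 | 298–293 | 5.1–5.3% |
| One clinician per centre | 4 × 26 = 104 | 2.88 | 1.02–1.09 | 294–274 | 5.2–6.1% |
| All centres switch together and share a calendar-week effect | 26 | 11.54 | 1.11–1.53 | 271–196 | 6.2–11.3% |

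For a one-sided 5% test, which the 138 implies, the corresponding levels are 5.0–5.2%, 5.2–5.8% and 5.9–9.2%.

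**3. Check by simulation.** An unpaired patient-level t-test was run on 4,000 simulated trials of 300 patients, with week ICC 0.05. The rejection rates were 5.7% (8 clinicians), 6.8% (4 clinicians) and 11.8% (26 shared weeks). These are slightly above the formula, as expected when cluster sizes vary.

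**4. Stable differences between clinicians.** With a constant clinician effect only (ICC 0.05, no week effect), the simulated rate was 4.4% with 4 clinicians and 5.5% with 8. The simulation error is about √(0.05 × 0.95 / 4000) = 0.3 percentage points, so neither shows inflation. Each clinician serves both arms, so these differences largely cancel. Leaving them out of the model mainly costs precision.

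**5. Sample size.** Even the lowest effective N in the table, 196, exceeds both 138 and the two-sided 170. That is before dropout and at-goal exclusions, which the protocol does not quantify. If losses left only 138 patients over 26 shared weeks, m = 138/26 = 5.31, DE = 1.04–1.22 and the true two-sided level would be 5.5–7.5%.

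**The case against.** The strongest reply is that the effect may be negligible. The protocol speaks of the clinician, so the natural cluster is the clinician-week, and with one to three patients in each the true level stays close to 5%. The top figure of 11.3% needs patients at four separate centres to be correlated merely because they enrolled in the same calendar week, although the outcome is six months of refills. Nothing in the protocol says that the centres switch in step. This stands, and that row should be read as an extreme.

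A reader might infer that the planned error bars are simply wrong. The documents do not support that. Inflation requires week-to-week variance, which is unknown, and omitting stable centre or clinician differences pushes the interval the other way. A reader might also infer that the trial is underpowered because of clustering. No shortfall is shown at 300 patients before losses.

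It can also be said that section 8 is a general paragraph that does not name the primary endpoint, and that model details belong in a statistical analysis plan. The choice of model could indeed be left there. But section 8 does not leave the method open: it names a paired test, the only between-group method the protocol states, and a later plan would have to contradict it.

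Finally, the more serious fault in the Randomisation paragraph is that the order is fixed and known before each patient is enrolled. That is true and is a separate issue. It does not make the analysis fit the design.

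**Conclusion.** The mismatch is in the text. Allocation is by clinician-week, while the stated test and the sample size take no account of that unit, and the stated test is paired although the groups are unmatched. The first consequence is certain: the test as named cannot be applied to the arm comparison without a pairing that the protocol does not define. The second is conditional: an unpaired patient-level t-test would understate the standard error to the extent that outcomes vary by week.

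Under the assumed ICC of 0.01–0.05 that second effect is small in the likelier patterns (true level about 5.1–6.1%) and material only if all centres switch together and share a week effect (up to about 11%). These figures rest on the assumed ICC and clinician counts, 26 enrolment weeks, all 300 patients analysed, and continued alternation. The point should be corrected, but it is not evidence that the result would be invalid.

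**What to change.** If weekly allocation is kept:

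- In section 8, replace the paired t-test for the refill score with a linear mixed model: arm and centre (or clinician) as fixed effects, and a random effect for the unit actually allocated, with small-sample degrees of freedom. That unit is the clinician-week, or the calendar week if centres switch in step. A clinician-week term would not capture a week effect shared across centres, so the protocol should say which pattern applies.
- Record enrolment date, clinician and centre on the case report form. The baseline list in 4.2 names none of them.
- In 4.5, state the assumed ICC and the resulting design effect beside the 138.

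If concealed individual randomisation is adopted instead, use an unpaired comparison adjusted for centre; the week term is then not needed.

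The cost is analysis wording, up to three fields on the form if they are not already there, and possibly wider intervals. At ICC 0.05 the widening is √1.09 − 1, about 4–5%, with one clinician per centre, and √1.53 − 1, about 24%, in the extreme case. The mixed model does not remove selection bias from a predictable allocation, which needs its own remedy.

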4.3. Study outcome measures

Primary Endpoint

Rate of statin compliance, based on pharmacy refill records. Values per patient can range from 0-6 according to the number of refills.

Secondary Endpoints:

Rate of perceived side-effects from statin use, including muscle aches, fatigue, mental fog, and gastrointestinal upset.

4.4. Relevance and implications of the trial results

1. Low compliance with statin therapy is widely observed and limits the preventative potential of the therapy and results in increased ASCVD events
2. Empowering patients by allowing autonomy in clinical decision making may be an effective tool to increase long term compliance.

4.5. Sample size/Power calculation

This study is designed as a superiority trial. Based on prior literature, we estimate a 50% statin compliance rate with a standard deviation of 10% (2). We will set the minimal detectable effect at a 5% increase in statin compliance, with an $\alpha < 0.05$ and power of 0.9. Based on case-to-control ratio of 1:1, our total minimum sample size for the primary endpoint is 138. However, we will plan on a total sample size of 300 patients, to account for patients who drop out of the study as well as patients who will be excluded due to attaining an LDL-cholesterol of <2.6 mmol/L (100 mg/dL) on red yeast rice extract.

5. Participant entry

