1.1. Study overview diagram

4.2 Study protocol:

Patients meeting the study criteria will be enrolled at outpatient cardiology clinics at four centers: Lithuanian University of Health Sciences, Northway Medical Centre, Prienu Hospital, and Unomeda Medical Centre. The enrolment period will last six months, with an estimated 50 patients per month enrolled into the study, for a total of 300 patients.

Patients will be randomized to either the control group or the intervention group. Baseline variables will include demographic variables (age, gender, BMI, blood pressure, heart rate), medical history (hypertension, hyperlipidaemia, type 2 diabetes mellitus, tobacco use), laboratory variables (total cholesterol, HDL, LDL, triglycerides, AST, ALT, creatine kinase, and, vitamin D levels) and socioeconomic variables (education level, income level, rural or urban, and marriage status).

The control group will be provided reassurance through a short, semi-structured discussion on the excellent safety profile of statins, similar to a typical interaction between a clinician and patient. They will then be prescribed 30mg atorvastatin daily as a 30 tablets supply with five patient-initiated re-fills for 30 tablets each. Final follow-up in this group will occur at 6 months.

The intervention group will be offered a red yeast rice extract 20mg nightly to achieve a goal LDL-cholesterol of <2.6 mmol/L (100 mg/dL) in accordance with the 2019 ESC/EAS guidelines (9). Initial follow-up will take place in 2 months to assess the efficacy of their treatment. Patients who are not at the goal LDL-cholesterol will be prescribed 30mg atorvastatin nightly as a 30 tablets supply with five patient-initiated re-fills for 30 tablets each, with final follow-up after 6 additional months. Patients who are at goal on the red yeast rice extract will be recommended to switch to lovastatin 20mg nightly as a bio-identical substitute, but they will be excluded from further analysis.

In both groups, statin adherence will be assessed by pharmacy refill records at the final follow-up. A short, four question questionnaire (Appendix A) will be administered at this point as well. Final follow-up laboratory variables collected will include total cholesterol, HDL, LDL, triglycerides, AST, ALT, creatine kinase, and vitamin D levels.

Conversation guidelines for each clinical encounter in the intervention group are included in Appendix B.

Randomisation

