5.2. Inclusion criteria

1. Over 40
2. Moderate ASCVD risk
3. Decline statin therapy

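### The 10% SD behind the claimed 90% power is only 0.6 of a fill on the 0–6 endpoint and is not justified there; the minimum of 138 also rests on an unstated one-sided test

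*Protocol*

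**What the plan says.** Protocol section 4.5 sets out the calculation. The design is stated as "This study is designed as a superiority trial". The inputs are "we estimate a 50% statin compliance rate with a standard deviation of 10% (2", a smallest difference to be detected of 5 points, alpha below 0.05 "and power of 0.9". The result is "Based on case-to-control ratio of 1:1, our total minimum sample size for the primary endpoint is 138". The planned total is then raised to 300, to cover dropout and the exclusion of patients who reach the LDL goal on red yeast rice. No rate is given for either loss. Neither section 4.5 nor section 8 says whether the test is one- or two-sided.

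Section 4.3 defines the primary endpoint from pharmacy records: "Values per patient can range from 0-6 according to the number of refills". Section 4.2 shows where the six comes from: a "30 tablets supply with five patient-initiated re-fills for 30 tablets each", that is, one initial supply and five further ones (called fills below). Under section 5.2, patients enter the trial because they "Decline statin therapy".

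**The concern.** The SD is given as a percentage and is never translated to the 0–6 scale on which the endpoint is measured. On that scale it is very small. It describes patients who nearly all collect about half their supply, with almost nobody collecting nothing or everything. These patients have declined statins and must request each refill themselves, so some at zero and some at six are to be expected.

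The claim of 90% power for a 5-point increase depends directly on this number. If the true spread is wider, a null result could be read as showing that offering choice does not improve adherence, when the trial could have detected only a considerably larger effect.

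A second, smaller point is that the minimum of 138 does not follow from a two-sided 5% test, and a reader would not know that a one-sided test had been used.

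**Working it through.** **Inputs.** From section 4.5: mean 50%, SD 10 points, difference 5 points, alpha 0.05, power 0.90, ratio 1:1. From section 1.1: 300 patients, 150 per arm. From section 4.3: scale 0–6, so 50% is 3 fills, 10% is 0.6 fill and 5% is 0.3 fill. SDs above 10% are assumptions; the protocol gives no other value.

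**1. Reproducing the 138.** For two independent means, n per arm = 2 (z_α + z_β)² (SD/Δ)², with SD/Δ = 10/5 = 2.

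- One-sided: 2 × (1.645 + 1.282)² × 4 = 68.5, so 69 per arm and **138** in total. This matches (the t-test version gives 69.2, total 140).
- Two-sided: 2 × (1.960 + 1.282)² × 4 = 84.1, so 85 per arm and **170** in total (t-test version 85.03, total 172).

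With 138 patients, t-test power is 83.0% two-sided and 89.9% one-sided. With 300 patients and SD 10% it is 99.1% and 99.6%, so sidedness alone does not endanger the trial.

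**2. What SD 0.6 means on 0–6.** The variance is 0.6² = 0.36, the average squared distance from 3. The following bounds each hold separately:

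- A patient at 0 or 6 contributes 9, so their share is at most 0.36/9 = 4%.
- A patient two or more fills from 3 contributes at least 4, so their share is at most 0.36/4 = 9%. At least 91% must therefore be at 2, 3 or 4.
- Any patient not at 3 contributes at least 1, so their share is at most 0.36/1 = 36%. At least 64% must therefore be at exactly 3.

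For comparison, identical patients with six independent 50:50 fills would have an SD of √(6 × 0.25) = 1.22 fills, or 20.4%. An even spread over 0 to 6 gives 2.0 fills, or 33.3%. The maximum possible is 3 fills, or 50%.

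**3. Largest SD that keeps 90% power with 300 analysed.** SD_max = Δ √(n/2) / (z_α + z_β), with Δ = 5 and n = 150, so √75 = 8.66.

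- Two-sided: 5 × 8.66 / 3.242 = 13.36% (t-test 13.3%, or 0.80 fill).
- One-sided: 5 × 8.66 / 2.926 = 14.80% (t-test 14.8%, or 0.89 fill).

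At a mean of 3, these limits allow at most (0.1332 × 6)²/9 = 7.1% and (0.1476 × 6)²/9 = 8.7% of patients at 0 or 6.

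**4. Power and detectable difference, 150 per arm, t-test.**

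| SD | Power for 5 points, two-sided | One-sided | Difference detectable with 90% power, two-sided |
|---|---|---|---|
| 10% (protocol) | 99% | 99.6% | 3.8 points |
| 15% (assumed) | 82% | 89% | 5.6 |
| 20.4% (assumed) | 56% | 68% | 7.7 |
| 30% (assumed) | 30% | 42% | 11.3 |
| 40% (assumed) | 19% | 29% | 15.0 |

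**5. Effect of losses.** All of step 4 assumes that nobody is lost. The numbers left for analysis cannot be predicted from the protocol. As an illustration, the largest tolerable two-sided SD falls from 13.3% to 11.9% at 120 per arm and 10.9% at 100 per arm.

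**The case against.** The strongest reply is that no sum is wrong. The 138 follows exactly from the stated inputs with a one-sided test, and a superiority trial looking for an increase is compatible with one. The SD is attributed to a cited source that could not be consulted here, so it cannot be shown to be false. The 20.4% benchmark assumes independent fills. A patient who takes about half the tablets would refill roughly every second month and land near 3, and dependence of that kind can push the SD below 20.4%. The 50% might also mean a proportion of compliant patients rather than a mean of 3 fills.

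Much of this is fair, and it limits the claim. The 20.4% is a reference point, not a floor, and every SD above 10% is an assumption. But the bounds in step 2 need neither independence nor any outside source, and a citation does not show that the figure is a per-patient SD of fills in people who declined statins. The proportion reading makes matters worse: comparing 50% with 55% at 90% power needs 3,414 patients one-sided or 4,190 two-sided. Nor is the step from 138 to 300 a reserve against a larger SD, because section 4.5 assigns it to dropout and exclusions.

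**Conclusion.** The concern holds. An SD of 10% is mathematically possible on the 0–6 endpoint but unsupported there, and the 90% power claim depends on it. With all 300 analysed, the claim fails once the SD passes 13.3% two-sided or 14.8% one-sided. At a mean of 3, that is certain if more than about 7% (two-sided) or 9% (one-sided) of patients take none or all six fills. The true SD is unknown from the document. The power of 82% to 19% and the detectable differences of 5.6 to 15.0 points follow from assumed SDs of 15% to 40%, a two-sided two-sample t-test and no losses. The unstated one-sidedness of the 138 is a reporting fault with no practical effect at 300 if the SD were 10%. The point should be fixed, because it decides what a null result can be taken to show.

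**What to change.** Keep 300 patients and rewrite section 4.5:

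- State whether alpha 0.05 is one- or two-sided. If two-sided, correct the minimum under the current inputs to about 172.
- Replace the 10% SD with a per-patient SD justified in fills on the 0–6 scale, or show a range of SDs labelled as assumed, for example 15% to 40%.
- Replace the single claim of 90% power for 5 points with the detectable difference for each SD. Under that assumed range it is 5.6 to 15.0 points two-sided with all 300 analysed.
- State the assumed dropout and LDL-goal exclusion rates, and give the larger detectable difference at the numbers then left for analysis.

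The cost is one reworded paragraph and a less favourable stated detectable effect. No patients are added and no procedure changes.

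### The minimum of 138 in section 4.5 reproduces only with an undeclared one-sided 5% test; with a two-sided 5% test it gives about 83% power, and the minimum is about 170

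*Protocol*

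**What the plan says.** Section 4.5 opens with "This study is designed as a superiority trial". It assumes a compliance rate of 50% with a standard deviation of 10%, and continues: "We will set the minimal detectable effect at a 5% increase in statin compliance". Alpha is given as below 0.05, with no word on one or two sides, followed by "and power of 0.9". The result is: "Based on case-to-control ratio of 1:1, our total minimum sample size for the primary endpoint is 138".

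The section then enlarges the trial: "we will plan on a total sample size of 300 patients, to account for patients who drop out of the study", and also to cover intervention patients who reach the LDL-cholesterol goal on red yeast rice extract and so leave the analysis. It gives no rate for either kind of loss.

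Section 8 names the test: "Statistical comparisons will be undertaken using a paired Student's t-test (after log transformation if necessary"), or a nonparametric alternative. It too says nothing about sidedness and sets no significance threshold.

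**The concern.** A sample size stated with alpha 0.05 and no qualifier is normally read as two-sided. Read that way, the minimum and the power in section 4.5 do not belong together.

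Two things depend on which test is meant:

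- **If two-sided**, a trial that ends with 138 evaluable patients would be described as having 90% power when it has about 83%.
- **If one-sided**, the chance of falsely declaring the autonomy strategy superior is 5%, not the 2.5% that a two-sided 5% test allows in that direction, and the test could not conclude that the strategy lowers compliance. That is a choice to declare and defend, not one to be inferred by working back from a sample size.

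**Working it through.** **Inputs, all from section 4.5:** difference 5 points, standard deviation 10 points, alpha 0.05, power 0.90, allocation 1:1. The standardised difference is d = 5/10 = 0.5. The standard deviation is taken as given; whether it suits a refill count of 0 to 6 (section 4.3) is a separate question.

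**Formula, two independent means:** n per arm = 2(z_alpha + z_beta)² / d², which with d = 0.5 is 8(z_alpha + z_beta)².

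1. **Reproducing the plan's figure (one-sided 5%).** 8 × (1.645 + 1.282)² = 8 × 8.567 = 68.5, so 69 per arm and 138 in total. This matches exactly.

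2. **Two-sided 5%, same inputs.** 8 × (1.960 + 1.282)² = 8 × 10.51 = 84.1, so 85 per arm and 170 in total, 32 more than stated. The exact (noncentral t) calculation gives 85.03 per arm. Strict rounding makes that 86 per arm, or 172, but power at 85 per arm is already 89.99%, so the two totals differ only by rounding.

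3. **Power at 138.** d × √(69/2) = 0.5 × 5.874 = 2.937.
   - One-sided: Φ(2.937 − 1.645) = Φ(1.292) = 90.2% (exact t 89.9%).
   - Two-sided: Φ(2.937 − 1.960) = Φ(0.977) = 83.6% (exact t 83.0%).

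4. **Other routes to 138.** None of these gives it.

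| Reading | Total N |
|---|---|
| Two-sided 5%, 80% power | 126 |
| Two-sided 5%, 85% power | 144 |
| Wilcoxon (efficiency 0.955), 90% power | 146 one-sided, 180 two-sided |
| 5% read as relative (2.5 points), 90% power | 550 one-sided, 674 two-sided |
| Two proportions, 50% v 55%, 90% power | 3,414 (one-sided) to 4,268 (two-sided, continuity-corrected) |
| Paired t-test with d = 0.5, 90% power | about 36 pairs one-sided, 44 two-sided |

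5. **Power at the planned 300, before losses.** d × √(150/2) = 0.5 × 8.660 = 4.330. Two-sided: Φ(4.330 − 1.960) = Φ(2.370) = 99.1%.

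6. **Loss in the intervention arm only.** Assumption: all 150 controls remain evaluable. The standard error is 10 × √(1/150 + 1/n), where n is the number of evaluable intervention patients.
   - n = 60: standard error 1.528; 5/1.528 = 3.273; Φ(3.273 − 1.960) = 90.5% (exact t 90.3%; at 59 it is 89.9%).
   - n = 75: 94%. n = 50: 86%.
   - n = 45: standard error 1.700; 5/1.700 = 2.942; one-sided Φ(1.297) = 90.3%, two-sided Φ(0.982) = 83.7%.

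   So about 45 evaluable intervention patients are enough for 90% power one-sided, but about 60 are needed two-sided. The loss that this arm can absorb falls from 105 of 150 (70%) to 90 of 150 (60%).

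**The case against.** **The figure is not an arithmetic slip.** It follows exactly from the section's inputs under a one-sided test, and the wording leans that way: a superiority design, an increase in compliance, and a hypothesis (section 3) that autonomy makes compliance more likely. This stands in part. It makes one-sided planning plausible, and a reader should not infer that the authors miscalculated. But directional hypotheses are routinely tested two-sided, a superiority label does not fix the sidedness, and nothing in the protocol declares the one-sided choice.

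**Sidedness may be in the statistical analysis plan.** Section 8's silence alone is therefore not a fault. The figure in 4.5 is different, because it already depends on the choice. A plan specifying a two-sided test would contradict it. A plan specifying a one-sided test would be the first place where the reader learned of it.

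**The trial recruits 300, not 138.** This stands and limits the severity. A reader might infer that the trial is underpowered. Under the protocol's own inputs the documents do not support that: two-sided power is about 99% before losses, and no loss rate is given from which to argue otherwise.

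**Conclusion.** The point holds as a mismatch inside section 4.5. The stated minimum of 138 and the stated 90% power agree only under a one-sided 5% test that the protocol does not declare. Under a two-sided 5% test, 138 gives about 83% power and the minimum is about 170 to 172. This rests on the protocol's own difference and standard deviation and on a comparison of two independent arms. That a bare alpha of 0.05 means two-sided is convention, not the protocol's text.

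Severity is moderate. The recruitment target need not change, but 138 is the floor against which 300 is justified, and that floor is too low if the test is two-sided.

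Two further inferences should not be drawn:

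- **A tolerable loss of 43% (from 300 to about 170).** The protocol states no loss allowance, and that figure assumes equal loss in both arms. Exclusion for reaching the LDL goal happens only in the intervention arm. If all loss fell there, 90% two-sided power would survive only 90 losses, which is 30% of 300.
- **That the two-month delay before atorvastatin makes lower compliance likely, so that a one-sided test is especially harmful here.** Sections 1.1 and 4.2 count compliance over six months from the start of atorvastatin in both arms. The delay does not shorten the refill window, and nothing in the protocol supports the inference.

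**What to change.** In section 4.5, state a two-sided alpha of 0.05 and restate the minimum as about 170 to 172 (85 to 86 per arm), leaving the target at 300. State the same sidedness for the primary test in section 8, or in the statistical analysis plan if one exists. If 138 is kept, either declare and justify the one-sided 5% test or report its two-sided power as 83%.

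Do not add a single percentage as a loss allowance. A more useful sentence says that, if all 150 controls remain evaluable, about 60 evaluable intervention patients are needed for 90% two-sided power under the stated inputs.

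The cost is two or three sentences and no additional patients.
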